## **Introduction/background**

Influenza and pneumonia are the most common infection-related and vaccine-preventable causes of hospitalization and death. 90% of influenza-related deaths occur among adults aged >65 years. Over 2 million Americans reside in nursing homes, skilled nursing facilities, or long term residential care facilities and this number is expected to expand significantly in the coming decades according to the CDC. These are among the highest risk and debilitated seniors that may acquire influenza. Two influenza vaccines are now available that are FDA approved specifically for persons over age 65: the newly approved adjuvanted seasonal influenza vaccine (Fluad) and the high dose (HD) vaccine that was approved in 2009 and is increasingly being used. The absolute or relative clinical advantage to long-term care residents of Fluad vs. HD over standard dose (SD) vaccine remains unclear from existing immunologic and clinical evidence.

For Year 2, we will be adding a 3rd vaccine substudy, recombinant FLUBLOK. FLUBLOK is a newer FDA approved influenza vaccine that has a higher amount of HA in the formulation than SD, and has a unique feature of not being produced in eggs. None of the three vaccines have been compared head-to-head and an industry-sponsored study is unlikely to be conducted to evaluate relative efficacy or effectiveness due to uncertainty as to whether manufacturers will gain additional market advantage while risking uncovering relative inferiority.

Both Fluad, HD, and FLUBLOK vaccine have been shown to be more effective than SD vaccine in trials conducted in different cohorts. HD vaccine and FLUBLOK are more expensive than SD vaccine, and Fluad is less expensive than HD vaccine. As an adjuvanted vaccine, Fluad has been shown to have higher levels of heterologous immunity to drifted influenza strains than non-adjuvanted (SD) vaccine - another potential advantage of Fluad over HD vaccine, which is non-adjuvanted. This project's rationale and innovation derive from its ability to determine the best use of these two vaccines in the setting of one of the most vulnerable elderly populations - those living in nursing homes (NH) and other various long-term care institutions.

### **Increased response to HD over SD influenza vaccine in geriatric adults**

In 2009, HD influenza vaccine consisting of 4 times the antigen of SD vaccine was licensed for use in persons over the age of 65. In studies prior to its approval, the anti-influenza titers as determined by HAI were significantly higher in the HD vaccine group than the SD group (Falsey et al., 2009).

Clinical efficacy of HD vaccine has been demonstrated in a large clinical trial (n=31,989) in which HD vaccine was 24.3% better at preventing laboratory confirmed influenza than SD vaccine overall (DiazGranados et al., 2014). A retrospective cohort study of 2.5 million Medicare recipients demonstrated that HD was 22% more effective than SD at prevention of probable influenza based on diagnosis codes and treatment and 22% more effective at prevention of influenza hospital admissions in older adults (Izurietta et al., 2015). A VA-wide retrospective study using the national VA database only showed benefit of HD over SD in veterans age 85 and older (Richardson et al., 2015), but notably employed a differently defined clinical endpoint than the other clinical efficacy studies (hospitalizations with a primary diagnosis of pneumonia or influenza without any requirement of lab confirmation or treatment regimen). We ran a pilot study in NHs and found the HD vaccinated group were 30% less likely to have any hospitalization compared with the SD group (adjusted relative risk 0.701; 95% CI: 0.543, 0.905; p=0.006) in an A/H3N2 dominant season (unpublished).

### **Increased response of Flud over SD influenza vaccine in geriatric adults**

Flud has not been tested in a large RCT with laboratory confirmed documentation of prevention of disease as HD vaccine has been. There are, however, multiple studies that support greater protective efficacy from Flud than SD. Mannino et al showed in a large cohort study conducted in Italy over 3 seasons that the risk of hospitalization from influenza or pneumonia was 25% lower in patients receiving Flud relative to SD vaccine (Mannino et al., 2012). This difference in protection is very similar to that observed in two of the HD vs. SD studies discussed above. Other studies focusing on nursing home patients including VanBuynder et al demonstrated in a case control study that Flud was superior to non-adjuvanted vaccine in protection from disease (Van Buynder et al., 2013), and Iob et al found that Flud was superior in effectiveness to the conventional vaccine, reporting protection rates of 80% vs. 57% respectively (Iob et al., 2005).

### **Increased Efficacy of FLUBLOK in adults**

Dunkle et al performed a large RCT enrolling individuals age 50 and older comparing FLUBLOK and SD vaccine (Dunkle, et al, 2017). They found the probability of influenza-like illness was 30% lower with FLUBLOK than with SD Quadravalent vaccine (95% confidence interval, 10 to 47; P = 0.006) and satisfied prespecified criteria for the primary noninferiority analysis and an exploratory superiority analysis of FLUBLOK over SD.

## **Justification/rationale/significance of the study**

### **Scientific Rationale**

As the primary endpoint we are using pre- to post-vaccine changes in HAI titers to compare seroconversion rates and post-vaccination HAI titers to calculate the ratio of the geometric mean titers in the two treatment groups. HAI is an in vitro bioassay that determines a subject's serum levels of anti-influenza antibodies. The FDA uses this as a standard immunogenicity assay for licensure. We will follow the guidelines set out in the FDA guidance document discussing non-inferiority immunogenicity studies. As additional methods to assess immunogenicity we are adding an assessment of anti-NA by performing NA inhibition assays (NAI) and SVN assays. Dunning et al recently supported the use of NAI and SVN assays as a correlate for protection in a trial of geriatric subjects (Dunning et al., 2016). Memoli in a healthy human challenge model showed that NAI is more predictive of protection and reduced disease than HAI (Memoli et al., 2016).

In the large HD vaccine clinical efficacy trial (n=31,989) one third of subjects also had immunogenicity data that allowed looking for correlations of immune assays with protection (DiazGranados et al., 2014). Their conclusions were that HAI and other immune assays are potential correlates of influenza vaccine protection in older adults, and that the protective thresholds for the HAI assay in the elderly appear consistent with those previously described for younger adults, provided the assay virus matches the circulating virus (Dunning et al., 2016).

### **Significance**

Data compiled by CDC in 2011-2012 showed that there were 1,383,700 residents in NHs. Also about 4,742,500 patients received services from home health agencies, and 1,244,500

patients received services from hospices, collectively accounting for much of the frailest in the US. Overall, these provider sectors served over 8 million people annually (2013). Our study will focus on residents in long term care (LTC) facilities, but the findings of our study are highly relevant to persons frail enough to require such services in all of settings where the vast majority are at least 65 years old and thus appropriate for Fludax or HD, influenza vaccines licensed for this age group.

The SD influenza vaccine has diminished efficacy in the older population with the more debilitated LTC residents being among the worst responders yet with the highest mortality. Deaths due to pneumonia and influenza and chronic lung disease were 20 times higher among NH residents compared to community residents (Menec et al., 2002). **The current availability of two vaccines specifically for the elderly that both appear to work better than SD vaccine begs the question: is the newer and less-costly Fludax vaccine non-inferior or even superior to HD vaccine?** The proposed study aims to initially address non-inferiority as this is feasible in the clinical trial R01 grant structure and a critical first step to obtain head-to-head data from the same trial, cohort and vaccine years. Our proposed study itself may provide direct guidance on vaccine usage or inform a future trial assessing actual superiority should that be appropriate based on the results of our study.

HD vaccine is increasingly used by older Americans despite its greater cost over the SD vaccine and no preferential recommendation by the Advisory Committee on Immunization Practices (ACIP), the CDC committee responsible for making the vaccine recommendations for the U.S.. A finding of non-inferiority in the primary endpoint would provide a strong rationale to consider using Fludax over HD that could result in some cost avoidance across large long-term care system in the U.S. We are not powered for a superiority analysis but in a non-inferiority trial if the findings are substantial enough they may show superiority.

In the normal seasonal setting, influenza strains drift antigenically and therefore vary from year to year. The CDC's prediction many months before the vaccination season sets the composition for the next season's vaccine, but does not always correctly anticipate the exact strain match that eventually actually circulates. We have Medicare claims data and modeling in the NH population that there is a significant increase in death and hospitalization in bad match over good match years particularly when A/H3N2 predominates (Pop-Vicas et al., 2015). In those mismatched years in particular, heterologous immunity or immunity to other non-exact match strains becomes much more important if the vaccine is going to provide any benefit that season. Fludax is an adjuvanted vaccine that has been shown to have a more broad-based or heterologous immunity than SD vaccine that is not adjuvanted (Ansaldi et al., 2008; Frey et al., 2014). HD is also not adjuvanted. Broad based immunity is especially desirable for A/H3N2 immunity as that has had 4 different circulating strains in the last 5 years while circulating A/H1N1 has been the same for 5 years; i.e., vaccine mismatch is more likely with the A/H3N2 circulating strain. A/H3N2 is associated with the majority of influenza hospitalizations and death among the elderly (Centers for Disease and Prevention, 2010).

For the recombinant FLUBLOK arm, there is emerging data that indicates that the method of producing the vaccine may be highly clinically significant. There are important egg-induced mutations in the production process of the recent A/H3N2 strains. The egg-produced vaccines induce antibodies to A/H3N2 that have substantially less blocking ability to wild type circulating A/H3N2 than do antibodies elicited by FLUBLOK, that is produced from a wild type sequence without mutations (Zost et al). If this deleterious issue of egg-adapted mutations continues, there may be a major push in the future toward non-egg-produced vaccines such as

FLUBLOK, and away from egg-produced vaccines such as both HD and AD. This could result in a change of production methods that shy away from egg-based vaccines. This supports the need and significance for having head to head comparative studies of FLUBLOK, HD and AD.

### **Purpose, including specific aims and/or hypotheses**

**Hypothesis:** Adjuvanted flu vaccine, Flud, is not immunologically inferior to HD influenza vaccine in older persons living in long-term care.

#### **Objectives:**

##### **Primary:**

To determine if Flud is immunologically non-inferior to HD flu vaccine in long term care residents over age 65.

As the primary endpoint we will evaluate the hemagglutinin inhibition (HAI) titer rise following vaccination to assess overall differences and seroconversion rates (4-fold rise in antibody titer) and post-vaccination geometric mean HAI titer of at least 40 in the treatment groups. HAI is an *in vitro* bioassay testing subjects' sera for specific anti-influenza antibodies to each strain in the vaccine. The FDA uses this as the standard immunogenicity assay for licensure. We will follow the guidelines set out in the FDA guidance document on non-inferiority immunogenicity studies for the analysis plan. We will also perform neuraminidase inhibition (NAI) assays and serum virus neutralization (SVN) assays there are recent data that NAI and SVN assays may be a better correlate of protection than HAI.

##### **Secondary:**

Aim 2: Secondary objective: To determine if Flud has greater heterologous immunity than HD vaccine.

HAI, NAI, SVN assays will be performed with heterologous A/H3N2 strains to determine if Flud has an increased breadth of both B and T cell responses as would be predicted from an adjuvanted vaccine.

Aim 3: Pilot clinical objective: To determine if Flud has similar protective efficacy to HD vaccine. We will perform a record review and obtain blood 2-4 weeks after the influenza season is over. From a record review and speaking with the Director of Nursing, we will obtain dates and diagnoses of influenza, hospitalizations, any "influenza like illness" (ILI), and other illnesses, diagnostic tests, and hospitalizations during the study participation period. From the remote blood sample, we will determine if there is serologic evidence of influenza infection with a 4-fold titer rise beyond the post-vaccine titers. In exploratory analysis we will compare efficacy of prevention of influenza infection of Flud vs. HD using the record review and laboratory assessments. We will also be able to examine the concordance in this long term care population between record review and titer rise methods as evidence of infection that may aid in future study design.

Aim 4: Pilot objective: To compare the immunogenicity of recombinant flu vaccine (FLUBLOK) to the AD and HD influenza vaccines.

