### **Data analysis plan**

#### **Study Outcome Measures**

As the primary endpoint we are using pre- to post-vaccine changes in hemagglutinin inhibition assay (HAI) titers to compare seroconversion rates and post-vaccination HAI titers to calculate the ratio of the geometric mean titers in the two treatment groups. HAI is an in vitro bioassay that determines a subject's serum levels of anti-influenza antibodies. The FDA uses this as the Gold Standard immunogenicity assay for licensure. We will follow the guidelines set out in the FDA guidance document discussing non-inferiority immunogenicity studies. SVN and NAI assays will be evaluated using the same methods.

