### **Analysis Plan**

The FDA guidelines (listed above) for demonstrating non-inferiority for a seasonal flu vaccine dictate the analysis of the co-primary endpoints. The ratio of the geometric mean titers will be assessed using tests of means on the log-transformed titers. The upper limit of the 95% CI of the difference (HD – Fluad) in the mean log titer will be compared to  $\log(1.5)$ . The difference in the seroconversion rates will be assessed with a two-sample proportion test. The upper limit of the 95% CI of the difference (HD – Fluad) in the seroconversion rates will be compared to 0.1. These analyses will be performed on HAI titers of all three strains obtained from studies of pre- and post vaccination serum.

For practical recruitment purposes we have to run the study over 2 years to recruit sufficient numbers of the full cohort for A/H3N2 analysis based on the sample size calculation. At the conclusion of our study, we can summarize the A/H3N2 HAI titers and seroconversion for each year separately; but our non-inferiority hypothesis is powered based on combining the years to include the total enrolment for the A/H3N2 analysis. Since we will recruit enough subjects each year due to small number of subjects needed to power the A/H1N1 analysis, we will perform and report separate analysis for each year studied as well as combining the data. For the B strain we are underpowered and will combine the two years for this exploratory result.

We will perform analyses on the other assays (NAI and SVN) on samples obtained at pre- and post- vaccination from all 3 strains. We will run HAI on all 3 strains for the post-season blood draw for Aim 1 as a secondary analysis for differences in the ability of titers to hold in one vaccine vs. the other for the length of the season. We will also run the NAI on the A/H3N2 only (for feasibility to keep assay number reasonable) on the post-season sample to assess if there are differences in maintaining anti-NA titers between the two vaccines. Any statistical tests performed for these assays are not powered to detect superiority or non-inferiority while preserving our study-wise error rate and will be considered exploratory in nature.

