Blood draws will be analyzed for humoral and cell mediated immune assays to determine flu-specific cells and antibody titers and immune status. Cells may be analyzed by RNAseq analysis to correlate aging immune responses and immune responses to the vaccines. We will not be making any DNA or doing any DNA gene analysis. No identifiable raw RNAseq files will be released that could be transcribed back to DNA for gene analysis purposes.

Analysis of FLUBLOK will be performed using the HAI and SVN assays as above and compared to the adjuvanted and high dose vaccines. NAI assays will not be used for this vaccine as it does not contain HA. If the pilot data are not powered by full non-inferiority studies we will also use Mann-U non-parametric tests to study differences in the mean responses between the vaccine groups.

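### Aim 2 draws a T-cell conclusion from three serum antibody assays; the cell-mediated assays mentioned elsewhere are undefined and not tied to it

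*Combined protocol and SAP*

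**What the plan says.** All references are to the Combined protocol and SAP.

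- **Objectives, Secondary, Aim 2.** The objective is "To determine if Flud has greater heterologous immunity than HD vaccine". The means are given next: "HAI, NAI, SVN assays will be performed with heterologous A/H3N2 strains". The same sentence gives the inference to be drawn, namely whether Fluad has "increased breadth of both B and T cell responses as would be predicted from an adjuvanted vaccine".
- **Study Outcome Measures.** The plan describes its lead assay thus: "HAI is an in vitro bioassay that determines a subject's serum levels of anti-influenza antibodies". It adds that "SVN and NAI assays will be evaluated using the same methods".
- **Analysis Plan.** The HAI comparisons, and the NAI and SVN analyses, are set out for the three vaccine strains. Heterologous strains are not mentioned. Tests on the other assays "are not powered to detect superiority or non-inferiority while preserving our study-wise error rate and will be considered exploratory in nature". Later in the section: "Blood draws will be analyzed for humoral and cell mediated immune assays", with RNAseq on cells as a possibility.

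**The concern.** Aim 2 runs from assay to conclusion in a single sentence, and the conclusion is wider than the assays. Antibody titers can speak to the B-cell response through its product. They cannot speak to T cells. A reader who follows the plan literally would take a favourable set of heterologous titers as evidence of T-cell breadth.

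This matters because the Introduction and the Significance section present broader immunity to drifted strains as a potential advantage of Fluad over HD. A T-cell claim would add weight to that argument without any data behind it.

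A smaller gap accompanies it. The aim asks whether Fluad is greater, but the plan never says what comparison of heterologous titers would answer that.

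**Working it through.** The documents state no figure for Aim 2, so there is none to reproduce. The check is mainly a comparison of sections.

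**Step 1: what the named assays measure, in the plan's own terms.**

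| Assay | Plan's description | Section | T-cell information |
|---|---|---|---|
| HAI | serum anti-influenza antibody | Study Outcome Measures | none |
| NAI | assessment of anti-neuraminidase response | Scientific Rationale | none |
| SVN | serum virus neutralization | Objectives, Primary | none |

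Changing the test virus to a heterologous A/H3N2 strain changes which antibody is detected. It does not turn a serum assay into a cellular one.

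**Step 2: whether T-cell data come from elsewhere.** The only candidate is the Analysis Plan statement on cell-mediated assays. To support Aim 2 it would need to supply the items below.

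| Needed for a T-cell breadth conclusion | In the plan? |
|---|---|
| Named T-cell assay and readout | No; only flu-specific cells in general terms |
| Heterologous A/H3N2 stimulus | No |
| Comparison of Fluad with HD | No |
| Link to Aim 2 | No |

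T-cell data may therefore be collected, but the plan does not make them the basis of Aim 2.

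**Step 3: whether a heterologous antibody analysis is specified.** Aim 2 names the assays and the A/H3N2 subtype. The Analysis Plan covers the three vaccine strains only. No heterologous endpoint or criterion for greater immunity is given.

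**Step 4: whether the antibody half could be answered with the planned type of interval.** The Analysis Plan uses a two-sided 95% CI on the difference in mean log titer, HD minus Fluad. That interval shows higher Fluad titers when its upper limit is below 0, which requires an observed Fluad/HD ratio above

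exp(1.96 × SD × √(2/n)).

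Inputs: n = 243 per group, from Sample Size Considerations. That number was set for the vaccine-strain A/H3N2 titer analysis; none is given for heterologous testing. The documents give no SD of ln titer, so 1.0 to 2.0 is assumed. √(2/243) = 0.0907.

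- SD 1.0: exp(1.96 × 1.0 × 0.0907) = exp(0.178) = 1.20 (rounded)
- SD 2.0: exp(1.96 × 2.0 × 0.0907) = exp(0.356) = 1.43

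Power for a true Fluad/HD ratio R is Φ(ln R / (SD × 0.0907) − 1.96):

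| True ratio | SD 1.0 | SD 2.0 |
|---|---|---|
| 1.5 | 99% | 61% |
| 1.25 | 69% | 23% |

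A conclusion of greater antibody immunity is thus attainable, with power that depends heavily on the unknown SD. No value of n or SD helps the T-cell half.

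**The case against.** **T-cell work is planned.** The Analysis Plan provides for cell-mediated assays, so one could call this a missing cross-reference. That stands in part: it would be wrong to say the trial will hold no T-cell data. But Aim 2 assigns the T-cell inference to HAI, NAI and SVN, and the cellular assays have no stated readout or heterologous stimulus that would let them take its place.

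**The aim is secondary and the tests are exploratory.** This also stands, and it keeps the point small. An exploratory label lowers the weight of a result, but it does not make an antibody titer informative about T cells. Nor does the label expressly reach heterologous HAI.

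**A stronger reading is tempting.** A reader might infer that Aim 2 is sent to the non-inferiority limits and so cannot support any conclusion of greater immunity. The inference would rest on "SVN and NAI assays will be evaluated using the same methods", which comes just after "We will follow the guidelines set out in the FDA guidance document discussing non-inferiority immunogenicity studies". The documents do not support it:

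- The sentence on SVN and NAI names no margin and no heterologous strain. It can equally mean the same summaries, that is, seroconversion and the GMT ratio.
- The limits of 1.5 and 10% appear in Sample Size Considerations and the Analysis Plan, where they belong to the HAI co-primary endpoints.
- The planned interval can show superiority as well as non-inferiority. The plan recognises this: Significance leaves a superiority finding open, and Sample Size Considerations expects one for A/H1N1.

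Nothing in the text suggests that a met non-inferiority limit would be reported as greater immunity. What remains is that the heterologous comparison is unspecified. Alone, that would be missing detail rather than an error.

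**Conclusion.** The point holds for the T-cell half of Aim 2, which is wrong as written: the named assays cannot yield the stated conclusion, and the plan supplies no linked alternative. This rests on the plan's own descriptions of the assays and on no numerical assumption.

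The antibody half is sound in principle and lacks only a stated heterologous comparison. The calculation in step 4 supports that statement and nothing more, since its SD is assumed and its sample size is borrowed from another analysis.

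Priority is low. The primary non-inferiority analysis, the sample size and the conduct of the trial are unaffected. What changes is what the trial may claim about breadth of immunity.

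**What to change.** Amend Aim 2 in one of two ways:

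1. Limit the conclusion to breadth of the antibody response to heterologous A/H3N2, and remove the reference to T cells.
2. If the cell-mediated assays already planned will include heterologous A/H3N2 stimulation, name the assay and its readout in Aim 2 as the only source of T-cell evidence, and keep HAI, NAI and SVN for antibody.

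In the same edit, add to the Analysis Plan that greater heterologous antibody immunity for Fluad will be judged by the upper limit of the two-sided 95% CI for the HD/Fluad heterologous GMT ratio lying below 1.0, and that this analysis is exploratory. It is needed because that section now covers only the three vaccine strains.

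Cost: about two sentences. The first option needs no new assays, samples or subjects. The second applies only if the heterologous stimulation is already intended, and then needs only its description.

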### **Study design including population to be studied, recruitment procedures and available resources**

We propose a non-inferiority randomized clinical trial to enroll 500 Long Term Care residents age 65 and older to receive either Fluvad or HD vaccine at 1:1 ratio. Blood will be sampled pre- and post-vaccine and post-influenza season and coded for blinded laboratory analysis. The FLUBLOK pilot objective will be a substudy of the current AD Fluvad vs. HD Fluzone study (UH IRB 10-27-29), and subjects will be consented on a separate FLUBLOK ICF.

**Population:** 500 subjects age 65 and older living in long-term care facilities in Northeast Ohio area. Up to an additional 120 subjects will be added to FLUBLOK substudy.  
50:50 male:female ratio.

**Study Duration:** 3 years

**Subject Duration:** estimated 6-8 months with patient contact

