We have received agreement currently from Seqirus (maker of adjuvanted vaccine), and are talking with Sanofi Pasteur (maker of high dose vaccine), to donate regular dose flu vaccine for use by employees at any participating LTC facility. This will be used as an incentive to the facility to agree to let us be a recruitment site. The vaccine will be sent directly from the manufacturer as a donation to the employee health team at the LTC site, so that we do not have to be involved in the handling, prescribing, or monitoring of the vaccine. If a LTC facility agrees to allow us to enroll, we will provide the manufacturer with the name and contact at the facility. We do not believe this is a coercive relationship with the long term care facility because they will get the vaccine once they agree to participate for the season, regardless of whether we recruit one or many from their site. We will also give all participating facilities an \$1000 participation stipend, to cover any administrative and staff costs that participation in the study may incur. The nursing and administrative staff (administrator, DON, ADON, Social Worker, Unit Nurses) at the long term care facility support the study in the following ways; they review the census with the study team during our initial meeting and prescreening, and help identify those residents that meet study inclusion criteria, and those residents that are not eligible for recruitment due to study exclusions. Additionally, the LTC administrative and nursing staff (Social Worker, Director of Nursing, Assistant Director of Nursing, Unit Nurses) helps the study team identify which residents can self-consent, and which ones utilize a LAR for their health care decisions. The LTC facility nurses and social workers, also helps the study team to identify residents (location), discusses medical conditions of the potentially eligible residents to determine if they are still eligible for recruitment or self-consenting, discusses medical conditions with the study team of consented residents to determine if they are still eligible at the time of vaccination, reviews the enrolled residents' medical conditions with the study staff at the end of study participation to determine if they had the influenza virus and/or other medical conditions that the study will be documenting for the study. The long term care facility also supports the study on the day of vaccination, by providing a nurse who helps identify consented residents. With regards to the administrative support, a designated nurse, the Director of Nursing, or the administrator at the LTC facility is in touch with the study staff throughout the duration of the study. The study coordinator sends regular updates, as to which residents

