After a resident is consented and found still eligible, they will be randomized using the UH based study database, RedCap, to receive one of the two licensed study influenza vaccines. Subjects will be assigned a donor code at that time that does not indicate which vaccine they have received so the lab analysis can remain blinded. Study staff will bring enough supply of each vaccine for either type of randomization and maintain the cold chain according to pharmacy policy so unused vaccine can be returned to the UH monitored study refrigerator. Vaccine will be given by research nurse or physician study staff or the clinical nurse at the long term care facility, since it is a standard of care vaccine that would have been given by that nurse even if they are not in the study. The first blood draw will be up to 2 weeks prior to the vaccine, or right before the vaccine is given. All blood draws will be obtained by the study research nurse.

Then at 4 weeks +/- 3 days we will return and draw the second blood draw. The third blood draw will be obtained 2-4 weeks after the influenza season is over, based on the CDC

surveillance in our region for that season when rates are near the offseason baseline. Typically that means the final blood draw will be sometime in April or early May of each season.

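### Only the laboratory is described as blinded, so the record-based part of the exploratory Aim 3 comparison is open to ascertainment that depends on the vaccine given

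*Combined protocol and SAP*

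**What the plan says.** **Blinding.** The Study design section says that samples from all three draws, including the post-season one, are "coded for blinded laboratory analysis". Study procedures adds that each subject receives a donor code "that does not indicate which vaccine they have received so the lab analysis can remain blinded". Neither section names any other party as masked, and nor does the rest of the protocol.

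**Giving the vaccine.** Study procedures states: "Study staff will bring enough supply of each vaccine for either type of randomization". It continues: "Vaccine will be given by research nurse or physician study staff or the clinical nurse at the long term care facility". No masked syringe and no separate unblinded vaccinator is described.

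**Clinical outcomes.** Under the secondary objectives, Aim 3 obtains dates and diagnoses of influenza, ILI, other illnesses, diagnostic tests and hospitalizations "From a record review and speaking with the Director of Nursing". Recruitment procedures describes the facility's part: its nursing and social work staff "reviews the enrolled residents' medical conditions with the study staff at the end of study participation to determine if they had the influenza virus".

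**Use of the data.** Aim 3 is labelled a pilot objective. Its comparison of the two vaccines on prevention of influenza infection is labelled exploratory and draws on both the record review and the laboratory work. The laboratory part is a fourfold rise over the post-vaccination titer in the post-season sample. Aim 3 also plans to check how well the record review and the titer rise agree.

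**The concern.** Diagnosis, testing and reporting of a respiratory illness all involve judgement, and the protocol gives no ILI case definition, testing trigger or adjudication step. Those who may know which vaccine a resident received also help to supply or classify that resident's events. If this knowledge affects what is recalled, recorded or called influenza, the arms can differ in recorded illness without differing in true illness, or a true difference can be hidden.

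The stake is limited but real. Aim 3 asks whether Fluad protects about as well as high-dose vaccine, and its concordance work is meant to inform the design of later studies. A record-based contrast that depends on knowledge of arm would be a weak basis for that, and the concordance check would take in the same distortion.

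**Working it through.** The protocol gives no event rate, effect size or power for Aim 3, so there is no figure to reproduce. The check is a reading of the relevant sections side by side.

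1. **Who is masked?** Study design and Study procedures both tie the coding to the laboratory. Residents, vaccinators, facility staff and record abstractors are not mentioned. The protocol does not call itself open-label, so the absence of wider masking is inferred from this silence together with the way the vaccine is given.

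2. **Who can know the arm?** Study staff carry both products and may give either. The vaccinator may instead be "or the clinical nurse at the long term care facility". Allocation is generated in RedCap, which is also where study data are entered. The Data/Sample confidentiality and security plans restrict RedCap to authorized personnel, but do not say which of them can see the allocation.

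3. **Who supplies and classifies the outcome?** Aim 3 relies on the records and the Director of Nursing. Recruitment procedures has facility nurses and social workers go through each resident's conditions with study staff to settle whether influenza occurred. The groups in steps 2 and 3 overlap: facility nursing staff and study staff appear in both.

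4. **Which endpoints does the overlap reach?**

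| Endpoint | Source | Exposed? |
|---|---|---|
| Co-primary HAI titer ratio and seroconversion | Coded samples, blinded laboratory | No |
| Aim 3 fourfold post-season rise | Coded samples, blinded laboratory | No |
| Aim 3 influenza diagnoses and ILI | Records and staff discussion | Yes |
| Aim 3 diagnostic tests and hospitalizations | Facility decisions, then records | Yes, through the decision to test or admit |

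5. **Does the serology cover the gap?** In part. It gives a blinded result by arm. However, the section on obtaining informed consent keeps subjects who refuse a blood draw in the study for data collection. For anyone without a post-season sample, the record-based outcome is the only Aim 3 information on infection.

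6. **Can the bias be sized?** If true risk is equal in the two arms, then

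   apparent risk ratio = (detection probability in one arm) / (detection probability in the other).

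   The documents give neither probability. Any number put in would return the assumption that produced it, so none is offered.

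**The case against.** The strongest case against raising this is that the plan already limits what it claims. Aim 3 is a pilot and its comparison exploratory. The confirmatory hypothesis is immunologic and rests on blinded assays. Aim 3 has its own blinded infection measure, and the planned concordance check could expose some misclassification. Both arms receive a licensed active vaccine, and nothing in the documents gives staff a reason to record illness differently by arm. The facility nurse is only one of the possible vaccinators. The updates sent to facilities are described as listing who consented, not who received which vaccine. All of this stands, and it keeps the point minor. It does not close the gap: the record-based component still enters the comparison, and nothing described keeps the allocation from those who classify it.

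Three stronger readings are tempting and are not supported:

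- **That Aim 3 is a comparison on ILI.** ILI is one of several items collected. The stated comparison is on prevention of influenza infection, using records and serology together.
- **That the staff who abstract outcomes see the allocation.** The protocol says who may enter RedCap, not who sees that field. They may know the vaccine; the documents do not say that they do.
- **That, with few events, even a small differential could create or hide a difference.** No event rate is given, and with few events chance would dominate.

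**Conclusion.** The concern holds in a narrow form. Blinding is described only for the laboratory, while influenza diagnoses, ILI and hospitalizations for Aim 3 come through facility and study staff who may know the vaccine given. That part of an exploratory comparison is open to arm-dependent ascertainment.

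A reader might infer that the trial's main conclusion is compromised. It is not: the co-primary HAI endpoints and the Aim 3 serologic endpoint are read from coded samples in a blinded laboratory. A reader might also want a figure for the bias, but neither its direction nor its size can be known from the documents.

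The verdict rests on two inferences: that masking not described is masking not planned, and that whoever gives a product, or works beside the person who does, can know what it was. As a change it is worthwhile because it is cheap, not because any primary result depends on it.

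**What to change.** Add a short paragraph to Aim 3 and the Analysis Plan covering these points:

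- Existing study staff abstract and classify Aim 3 events on a coded form, with the RedCap allocation field hidden from them. Where possible, they are not the staff who vaccinated that resident.
- One fixed ILI definition, written before abstraction starts, is used for every resident.
- The classification is locked before it is linked to arm.
- The blinded fourfold serologic result is reported by arm beside the record-based result. ILI known only from interview is treated as supportive.
- The report states that facility staff were not masked.

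The cost is a database permission setting, some care in assigning staff and a few sentences of text. No new staff, visits, assays or subjects are needed.

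The downside is that masking stays partial. Facility staff and some charts may still reveal the vaccine, and decisions to test or hospitalize remain unmasked. Restricting attention to laboratory-positive influenza or hospitalization would therefore not remove the problem, which is why the blinded serology belongs alongside.
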